#### Data Analysis

*Quantitative analysis:* Descriptive statistics were presented for baseline participant characteristics: means and standard deviations or medians and quartiles for continuous measures, and frequencies and percentages for categorical measures. All instrument measures at baseline and follow-up were summarized with appropriate descriptive statistics. The seven quantitative measures from the PHQ-9, PROMIS support instruments, and PPS-R were reported as unadjusted mean scores and their 95% confidence intervals (CIs) at each of baseline and follow-up, as well as for the changes from baseline to follow-up. We predicted with a sample size of 30, we would be able to detect medium effect sizes (Cohen's  $d=0.53$ ) of instrument change scores between the two time points (unadjusted type I error rate  $\alpha=0.05$ , power  $1-\beta=0.80$ ). SAS 9.4 will be used for all statistical analyses.

*Qualitative analysis:* We employed a constructivist grounded theory approach which is a well-known way to explicate processes, in this case change related to the intervention. Theory is "grounded" in the data themselves. Constructivist grounded theory therefore uses a combined inductive

and deductive approach, coupled with the recognition that study participants and researchers 'co-construct' data, thus making it a good fit for community-engaged research. As such, analyses require inclusion of participant perspectives and meaning to be fully developed. A key aspect of this approach is its iterative nature, thus analysis will be ongoing and begin at baseline. Beginning in Month 3, notes from audio recordings were checked for accuracy and imported into NVivo 11, a qualitative data analysis software program. [name] trained [name] in qualitative coding techniques and all qualitative data will be independently coded by [name] and [name]. Analysis began with 1) text-based coding, marking recurrent themes or statements, 2) as themes emerge, [name] and [name] met to define and standardize them, agree on a structural framework and to determine how themes should be applied to coding, 3) [name] and [name] used focused coding of prominent thematic clusters and constant comparison techniques to conduct preliminary analysis of prominent themes, 4) we conducted member checking through sharing these preliminary interpretations during Class 4, using methods developed by CBPR researchers to elicit feedback and interpretation from the group, which we then incorporated into our analyses. For Aim 1, qualitative analysis of narratives from class discussion and observational notes provided insights into women's explanatory models of MEH to inform the case management and resource access phase of the intervention, the dynamics of the structured dialogue group process, how women develop and use action plans to navigate and access resources, how they explain and describe their experience in this process, and the extent to which empowering processes emerge. For Aim 2, we analyzed challenges and barriers identified by participants and identify potential strategies to promote institutional and policy changes that would positively affect MEH through advocacy. Aim 3 was assessed by looking at evaluation process data for participant perspectives on the feasibility, acceptability, value and cultural appropriateness of the intervention model.

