**Aim 3. Assess the feasibility of the intervention.** We will track recruitment, attrition, attendance at group sessions, and attendance at individual CHW navigation meetings. We will gather survey data and qualitative data to document participant experiences with and perceptions of the group process, working with the CHW, and the value of the intervention. **Hypotheses:** The intervention we pilot will be feasible, acceptable, valuable, and culturally appropriate.

**Expected Outcome.** This pilot study will use team science to test an intervention that emerged organically in the community and contribute to building the next generation of health disparities research using knowledge generated through solution-based investigation as the foundation for submitting an NIH R21 research proposal.

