### **Approach**

Theoretical Model: The model in the study is informed by **socioecological approaches** to address disparities and affect change at **multiple levels** as broadly constructed by a **social and structural determinants of health framework.** We included attention to change at the level of the individual, the social group, and external infrastructure (e.g. political, legal, economic and other social/institutional factors). Our pilot addressed social and structural determinants at each of these levels.

Research Design: We use a **convergent parallel mixed method research design** to implement an intervention to affect **six domains of interest** in the lives of Latinas: 1) emotional support, 2) informational support, 3) depression, 4) social isolation, 5) empowerment, and 6) social determinants needs. Further, we will assess the feasibility of implementing this model with 30 participants. The intervention integrated navigation assistance and case management by a CHW with a peer support group. We gathered both qualitative and quantitative data using a variety of instruments and methods as described below, and we will integrate different types of data during analysis and interpretation.

Team Expertise & Roles: Our transdisciplinary team integrated expertise from anthropology, community-engaged research, social work, counseling, community navigation, and biostatistics, and we are well situated to conduct the proposed research. **[name] [name], the PI**, is a cultural anthropologist and Research Assistant Professor of Pediatrics in the Prevention Research Center. She has over 20 years’ experience conducting community-engaged research with migrants and other marginalized people to improve health and well-being. **[name], Principal Community Mentor and Co-Investigator**, was trained as a Special Education teacher in Aguascalientes, Mexico and

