**Population:** This project involved Spanish-speaking Latinas from low-income households. Participants was recruited from the International District and South Valley neighborhoods of Albuquerque and screened for language, self-reported ethnic identity as Latino/Hispanic, and self-reported income below 250% of the Federal Poverty Level. The majority of the participants were Mexican immigrants with one participant who was from Central America and one who was a second generation Mexican immigrant.

**Recruitment:** During month #2 prior to the start of the intervention, [name] recruited 30 participants through the Pathways Program, the Simplemente Salud Clinic and Centro Sávila. In the course of regular meetings with clients who request a range of services, she identified identify and invite those who might benefit from the proposed model. While participants experessed interest int eh program, lower numbers than anticipated joined the study from the first 3 cohort. We therefore changed the implementation strategy to allow for two sequential cohorts, one in the Fall and and one in the Spring.

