| Social Isolation         | PROMIS     | 8 items    | B&F        |
| Resiliency               | CD-RISC                 | 25 items   | B&F        |
| Adverse Childhood Events | ACES                    | 10 items   | F          |
| ACES Resiliency          | ACES + Resiliency       | 12 items   | B&F        |
| Eval & Feasibility       |                         | 8 items    | F          |

*Quantitative data collection:* Data was stored in a database created in UNM's secure data capture system, REDCap. We tracked recruitment, attrition, attendance at group sessions, and attendance at individual CHW navigation meetings. Pre-/Post-data was gathered at baseline (Class 1) and follow-up (Class 6) in the form of a multi-dimensional survey (see table). The survey will include: A) demographic questions to characterize participants, B) program evaluation/feasibility questions to document participant experiences with and perceptions of the group process, working with the CHW, and the value of the intervention, C) seven reliable instruments that have been validated in English and Spanish to measure the six domains of interest: a) emotional support, b) informational support, c) social isolation ; d) depression; e) ACES; and f) resiliency.

*Qualitative data collection:* Group class sessions were audio-recorded. [name] and/or [name] attended Classes 1 and 6 for each cohort and take observational notes. Analytical notes taken during team meetings. Notes from individual case management sessions, individual resource action plans, and the Advocacy Plan will be documented and analyzed.

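### Recruitment, attrition and attendance were named and tracked for Aim 3, but the stated analysis leaves them out and feasibility is concluded without a count

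*Combined protocol and SAP*

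**What the plan says.** Under Aim 3, the Specific Aims section sets out the feasibility measures: "We will track recruitment, attrition, attendance at group sessions, and attendance at individual CHW navigation meetings". Survey and qualitative data on participants' experience come in addition to these. The Research Design paragraph of the Approach gives the intended size: "we will assess the feasibility of implementing this model with 30 participants".

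The quantitative data collection paragraph confirms that the measures exist: "We tracked recruitment, attrition, attendance at group sessions, and attendance at individual CHW navigation meetings". The instrument table lists an 8-item "Eval & Feasibility" block, collected at follow-up only.

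In Data Analysis, the quantitative paragraph covers baseline characteristics, instrument scores with their changes, and a detectable effect size. Aim 3 appears once, in the last sentence of the qualitative paragraph: "Aim 3 was assessed by looking at evaluation process data for participant perspectives on the feasibility, acceptability, value", to which the sentence adds cultural appropriateness.

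The Recruitment paragraph says that the community health worker "recruited 30 participants through the Pathways Program" and two other sites. It then says that "lower numbers than anticipated joined the study from the first 3 cohort", and that the team therefore "changed the implementation strategy to allow for two sequential cohorts". The Results open by declaring the intervention acceptable and feasible. The Conclusions report that women found it hard to commit at the outset and that completing surveys in class was an obstacle, and they forecast strong participation if funding continued.

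**The concern.** Feasibility has two parts that need different data. Whether the women who took part valued the programme is a matter of perspective. Whether women can be recruited, kept and brought to sessions is a matter of counts. Aim 3 names both kinds of data, but the stated analysis carries through only the first.

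This matters because the narrative evidence on the second part is mixed. Low joining, a redesign of the cohorts, difficulty committing and poor survey completion all bear directly on feasibility. None is quantified, and none is carried into the verdict in the Results. The evaluation items also come only from women who reached follow-up, so anyone lost earlier has no voice in that survey. The pilot is meant to support a larger grant application, whose planners would need uptake and retention figures.

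**Working it through.** The plan gives no feasibility rate to reproduce, so the check is a comparison of sections.

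**Step 1. Follow each measure through the document.**

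| Measure | Named under Aim 3 | Said to be tracked | In quantitative analysis | In the Aim 3 analysis sentence | Any figure in the text |
|---|---|---|---|---|---|
| Recruitment | yes | yes | no | no | 30 |
| Attrition | yes | yes | no | no | none |
| Group attendance | yes | yes | no | no | none |
| Navigation attendance | yes | yes | no | no | none |

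Named: 4. Tracked: 4. Analysed: 0. With a figure: 1.

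**Step 2. Check the one figure.** Planned 30 (Research Design) minus recruited 30 (Recruitment) = 0. The same Recruitment paragraph says that joining fell below expectation and that the strategy changed as a result. At least three readings are open:

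- 30 women agreed and fewer joined. The number who joined is then not given.
- Early cohorts fell short and later ones made up the number, so 30 joined in the end. The paragraph places recruitment in month 2, before the intervention began, which fits this awkwardly but does not rule it out.
- The figure of 30 is the planned number, left in place when the text was updated.

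The cohort description does not settle it. The implementation section has cohorts of 10 and the timeline shows three (3 × 10 = 30), while the Recruitment paragraph moves to two sequential cohorts without giving their size.

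**Step 3. Who can answer the evaluation items.** The items are given at follow-up only. Respondents are therefore at most the women who reached follow-up, who are at most the women who joined. Neither count is given, so the share of joiners who were asked is unknown.

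**Step 4. What the counts could show.** With assumed retention of 18 of 30 (60%), the exact 95% confidence interval is 41% to 77%; with 24 of 30 (80%), it is 61% to 92%. These are illustrations, not estimates. They show that the counts would be informative but imprecise, which is one reason to report them descriptively.

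**The case against.** Several points on the other side have weight.

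- **The problems are disclosed.** Low joining, the changed strategy and the survey difficulty are all stated. This is true and to the authors' credit, but disclosure in narrative does not supply the counts or qualify the verdict.
- **The Results are a short summary.** They give no score, interval or sample size for any outcome, and the timeline lists a separate final report that is not among the documents. A reader might infer that the counts were never analysed, or that the verdict rested on perspectives alone. The documents support neither. They show only that the counts are absent from the stated analysis and from this text.
- **The process data might include tracking logs.** Possibly, but the sentence ties those data to participants' perspectives, and no other section analyses attrition or attendance.
- **The follow-up-only items do not prove bias.** This stands. Class audio and case-management notes may include women who later left.
- **There is no feasibility criterion.** This also stands. Counts would inform the verdict without settling it, and a threshold chosen now would be arbitrary.

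Two further inferences should be resisted. One is that recruitment failed: an early shortfall later made up is a possible reading. The other is that the pre/post comparison lost its power. The stated detectable effect of 0.53 reproduces with 30 complete pairs (0.529, two-sided test assumed). It is a planning figure for Aim 1, however, and the number of complete pairs is not given, so it is no evidence on this point.

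**Conclusion.** The point holds as an omission in the Aim 3 analysis and its reporting. Four feasibility measures were named in advance and tracked; none enters the stated analysis, and the feasibility conclusion is given without a count while the narrative describes recruitment and completion problems. As written, the conclusion is supported at most for acceptability among the women who took part and responded. Feasibility of recruitment and retention cannot be verified from this document.

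The size of any bias cannot be computed, because no numerator or denominator is given for attrition, attendance or survey completion. The finding rests on the supplied text only and assumes nothing about what the final report contains. It should be corrected, since it concerns one of the three aims and the data are said to exist.

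**What to change.** 1. Amend the Aim 3 sentence in Data Analysis to include the four tracked measures, reported descriptively with denominators in one table: joined against the planned 30, by cohort; retained to Class 6 out of enrolled; classes attended; navigation meetings attended; both surveys completed out of enrolled; evaluation items completed out of enrolled. Give joined out of invited only if invitations were logged. Confidence intervals are optional. The measures were named in advance, so mark only new denominators or table formats as added after the results were known. Apply no thresholds retrospectively.
2. In the Recruitment paragraph, reconcile the 30 recruited with the statement that fewer joined than expected. State how many agreed and how many joined, before and after the strategy change.
3. Until those counts are given, limit the Results statement to acceptability among women who took part and responded. Then word feasibility of recruitment and retention according to the reconciled counts, noting that the original cohort strategy was changed after low early joining.
4. Optionally, present the forecast of future participation in the Conclusions as an expectation that this study did not test.

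The cost is one small table from data already tracked and edits to four short pieces of text. Invitation counts may not be recoverable, because invitations were made during ordinary client meetings. The feasibility statement may become less favourable.

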## Results

Intervention was acceptable and feasible. Increase in resiliency was our most robust quantitative finding. Social, emotional and informational empowerment scores improved, but not in statistically significant way. Depression scores worsened, which could reflect the effectiveness of the psychoeducation component. Qualitative results: participants' experiences in the intervention underscored the importance of recognizing cultural differences in values and meaning related to MEH: 1) Self-advocacy and self-efficacy (learning how to say "no" or set limits as Latinas) ; 2) Addressing violence (in domestic settings, in families, social violence) ; 3) Isolation and socializing (recognizing differences in U.S. v. Latin America) . Overall, the results demonstrated the importance of multilevel interventions that address mental health at multiple levels: 1) Individual:

| Research Timeline                                | Month |   |   |   |   |   |   |   |   |    |    |    |
|--|-------|---|---|---|---|---|---|---|---|----|----|----|
|  | 1     | 2 | 3 | 4 | 5 | 6 | 7 | 8 | 9 | 10 | 11 | 12 |
| Activity   |       |   |   |   |   |   |   |   |   |    |    |    |
| Planning/Logistics                               | ■     |   |   |   |   |   |   |   |   |    |    |    |
| Recruitment                                      |       | ■ |   |   |   |   |   |   |   |    |    |    |
| Cohort 1 (Classes 1-4)                           |       |   | ■ |   |   |   |   |   |   |    |    |    |
| Quantitative Baseline Interview                  |       |   |   |   |   |   |   |   |   |    |    |    |
| Cohort 2 (Classes 1-4)                           |       |   |   | ■ |   |   |   |   |   |    |    |    |
| Cohort 3 (Classes 1-4)                           |       |   |   |   | ■ |   |   |   |   |    |    |    |
| Analysis of Class Data                           |       |   |   |   | ■ | ■ |   |   |   |    |    |    |
| Class 5 – Discuss Findings, Resource Access Plan |       |   |   |   |   | ■ | ■ |   |   |    |    |    |
| Individual Case Management                       |       |   |   |   |   |   | ■ | ■ | ■ |    |    |    |
| Class 6 – Follow-up to Discuss Outcomes          |       |   |   |   |   |   |   |   | ■ |    |    |    |
| Quantitative post-interview                      |       |   |   |   |   |   |   |   |   | ■  |    |    |
| Data Analysis of Outcome Class                   |       |   |   |   |   |   |   |   |   | ■  | ■  |    |
| NMPHA (Present Advocacy Plan)                    |       |   |   |   |   |   |   |   |   |    | ■  |    |
| Report results in Community Venues               |       |   |   |   |   |   |   |   |   |    |    | ■  |
| Final Report for TREE Center                     |       |   |   |   |   |   |   |   |   |    |    | ■  |

addressing stigma, recognizing the prevalence depression and anxiety, investing in self and life purpose, developing coping skills, self-esteem, agency/empowerment and emotional awareness. 2) Family: recognizing/helping other family members, redefining family in U.S. context; 3) Community: Providers-knowing who to see, what questions to ask; Organizational—what organizations offer, which are accessible. Finally, these results can inform administrative/systems/policy change to improve mental health equity for Spanish-speaking Latina women.

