## Specific Aims

Hispanic women (Latinas) experience mental and emotional health (MEH) concerns and disorders that often go unrecognized by health providers, and even when recognized, Latinas have low-levels of treatment follow-through with biomedical modalities. Using a novel community-directed, solution-based approach to increase access to existing services and nurture culturally meaningful social relationships, it is possible to address social determinants of health and reduce these disparities.

The **goal** of this study is to implement such an approach conceptualized by a community health worker (CHW) to pilot an innovative, multi-level intervention to address social and structural determinants that negatively influence MEH disparities for Latinas from low-income households. The proposed research integrates CHW navigation with group peer support. Both of these strategies have been shown to be culturally appropriate and effective for improving a variety of health outcomes with this population. Our transdisciplinary, community-engaged team will use a convergent parallel mixed method research design to assess the feasibility of the intervention and its impact on six domains of interest: 1) emotional support, 2) informational support, 3) depression, 4) social isolation, 5) empowerment, and 6) social determinants needs. As part of our preparation for future extramural funding, we will include development of an advocacy plan for multi-level social change impact.

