**Aim 1. Create a group navigation model to improve mental and emotional health equity for Spanish-speaking Latina women.** In a series of peer group sessions facilitated by [name], a CHW who designed the model, we will create a culturally-appropriate, non-stigmatizing group intervention. The group process will allow participants to explore their own MEH, better understand the ways that mental health influences well-being and everyday dynamics of their lives, and to develop empowering knowledge and action plans through the support of other women. We will document group discussions, processes, and themes, gather information about women's explanatory models of MEH, and administer a multidimensional survey to capture information about the domains of interest. Through individual case management, [name] will work individually with women from the groups to identify their specific social and structural determinants needs, assist them to make an individual action plan, provide them with information about available resources, and help them navigate systems and access resources and services. We will document participant needs and navigation outcomes. **Hypotheses:** Participation will decrease depression, social isolation, and social determinants needs, and increase emotional support, informational support, and women's sense of empowerment.

**Aim 2. Create an advocacy plan.** With data gathered in group meetings and individual navigation sessions, we will identify social and structural barriers that negatively influence participants' MEH outcomes and ability to access resources and services. We will create an advocacy plan to address structural and policy barriers that can be implemented by CHWs and advocacy groups in the future. **Hypotheses:** We can identify factors that negatively influence the MEH and well-being of Latinas. We hypothesize that in the future, we can use this knowledge to develop a strategic plan with the potential to address socio-structural and policy barriers through advocacy.

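### The planned change-score analysis does not match the instruments collected, and the lead result, resiliency, lies outside the Aim 1 hypotheses and is reported without figures

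*Combined protocol and SAP*

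**What the plan says.** **Hypotheses and domains.** Aim 1 in Specific Aims predicts: "Participation will decrease depression, social isolation, and social determinants needs, and increase emotional support, informational support". The sentence then adds empowerment. The opening of Specific Aims lists the domains as "1) emotional support, 2) informational support, 3) depression, 4) social isolation, 5) empowerment, and 6) social determinants needs", and Research Design under Approach repeats the list. Resiliency is in none of these places.

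**Survey.** Quantitative data collection, under Intervention Implementation, refers to "seven reliable instruments that have been validated in English and Spanish to measure the six domains of interest". The six it then names are emotional support, informational support, social isolation, depression, ACES and resiliency. ACES and resiliency thus stand where the other lists have empowerment and social determinants needs.

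**Analysis.** Quantitative analysis, under Data Analysis, first says that all instruments are summarised descriptively at both times. It then says that seven measures from PHQ-9, the PROMIS support instruments and PPS-R are reported as means with 95% confidence intervals at baseline, at follow-up and for change. The power statement is d=0.53 for change scores with 30 participants, unadjusted alpha 0.05 and power 0.80.

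**Results.** "Increase in resiliency was our most robust quantitative finding". Then: "Social, emotional and informational empowerment scores improved, but not in statistically significant way". Depression scores are said to have worsened. No estimate, interval or number analysed is given.

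**The concern.** Three parts of the document do not line up: what was hypothesised, what the change analysis names, and what is reported first. The lead result comes from a construct that Aim 1 does not mention and from an instrument that the change-interval sentence does not name. The label used for the non-significant results is that of an Aim 1 domain, empowerment, for which the table shows no instrument.

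This matters because Expected Outcome presents the pilot as the basis for an R21 application. A reader choosing outcomes for that application could take resiliency as a tested Aim 1 effect, or take the empowerment wording as survey evidence for the empowerment hypothesis. Without figures, nobody can tell whether the resiliency change was larger than the changes in the hypothesised scores.

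**Working it through.** **1. Set the table against the analysis sentence and Aim 1.** The PROMIS wording is taken generously, to cover all three PROMIS scores.

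| Score | Collected | Named for change intervals | In Aim 1 hypotheses |
|---|---|---|---|
| PHQ-9 | both times | yes | yes |
| PROMIS emotional support | both times | yes | yes |
| PROMIS informational support | both times | yes | yes |
| PROMIS social isolation | both times | yes | yes |
| CD-RISC | both times | no | no |
| ACES + Resiliency | both times | no | no |
| ACES (row "Adverse Childhood Events | ACES") | follow-up only | no | no |
| PPS-R | not in table | yes | cannot be told |

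Counts:
- Scores collected at both times: 4 + 2 = 6. ACES has no baseline and so no change score.
- Measures both named and tabled: 4. The stated seven leaves 7 − 4 = 3 that would have to come from PPS-R.
- Scores collected at both times but not named: 6 − 4 = 2, and both are resiliency scores.
- Aim 1 domains with a score in the table: 4 of 6. Empowerment and social determinants needs have none.

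**2. Reproduce the plan's power figure.** Paired t-test on the change, two-sided alpha 0.05 (sidedness is not stated). The noncentrality is d√n = 0.53 × √30 = 2.90 on 29 df. Power is 0.801, and the effect detectable with 80% power is 0.529. The stated 0.53 and 0.80 are reproduced. They apply per measure and do not depend on whether there are six or seven.

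**3. Precision of a mean change.** Half-width of the 95% interval, in SDs of the change, is t(0.975, n−1)/√n. Power is for d=0.53.

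| Pairs | Half-width | Power | Effect detectable with 80% power |
|---|---|---|---|
| 30 | 2.045/5.477 = 0.37 | 80% | 0.53 |
| 20 (assumed) | 2.093/4.472 = 0.47 | 61% | 0.66 |
| 15 (assumed) | 2.145/3.873 = 0.55 | 48% | 0.78 |

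The values 20 and 15 are assumptions, because the number with paired data is not stated. Recruitment says that 30 were recruited but also that fewer than expected joined from the first cohorts. Conclusions names survey completion in class as a barrier.

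A mean change is non-significant at two-sided 0.05 when it is smaller than the half-width. An improvement of just under 0.37 SD with 30 pairs, or just under 0.55 SD with 15, would therefore fit the Results wording. The words alone do not show by how much resiliency differed from the other scores.

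**The case against.** **Resiliency was planned for.** It is in the survey domain list, CD-RISC is scheduled at both times, and the general descriptive sentence covers every instrument. This stands. A reader might infer that resiliency was an unplanned measure or was outside the analysed set, and the documents do not support that. What remains is that the sentence promising intervals for change does not name it and that Aim 1 does not predict it.

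**Seven may be a correct count.** If PPS-R yields three scores, 4 + 3 = 7. The documents neither define PPS-R nor say how many scores it gives, so the number may reflect its subscales or be leftover wording. It would be too strong to say that seven is impossible. The firm point is that the sentence names an instrument missing from the table and omits two that are in it.

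**Empowerment may have been measured.** PPS-R might have been intended for empowerment or needs. A flat statement that these hypotheses have no survey score would go too far; only the table as it stands shows none. Qualitative analysis covers empowering processes, and for needs Specific Aims says: "We will document participant needs and navigation outcomes".

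**The empowerment scores are probably the three PROMIS scores.** That is likely, and they would then have moved as predicted without reaching significance. It is an inference, because Results does not name the instruments and gives no direction for social determinants needs.

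**The Results paragraph is a short summary.** It does not call resiliency an Aim 1 effect or statistically significant, Conclusions calls the results preliminary, and the final report in the Research Timeline may hold the figures. This limits the weight of the point but does not remove the mismatch in the plan itself.

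**Conclusion.** The point holds as a mismatch between plan, data and report. The change-interval sentence names PPS-R, which is not in the table, and leaves out both resiliency scores among the six collected at both times. The document carries two incompatible lists of six domains, and the lead result comes from the one that the hypotheses do not use. The ranking of resiliency cannot be checked, because instrument, estimate, interval and N are all missing. The empowerment label matches no tabled instrument.

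The counts rest on taking the table as complete. The precision figures rest on a two-sided paired t-test and, below 30, on assumed numbers of pairs. A reader might go on to infer that the resiliency increase is spurious or that the power calculation is wrong. The documents support neither: no resiliency figure is given to judge, and d=0.53 is reproduced. Nothing here bears on the feasibility findings or the qualitative results. The change should be made because it affects what can be concluded for Aim 1.

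**What to change.** 1. Reconcile the domain lists in Specific Aims (including the Aim 1 hypotheses), Approach and Quantitative data collection.
2. State whether PPS-R was collected.
   - If it was not, correct the Quantitative analysis paragraph by a dated note marked as made after the results were known. List the six scores collected at both times. Keep the mean and 95% interval at baseline, at follow-up and for change. Add the number of participants with paired data, and summarise ACES descriptively.
   - If it was, add PPS-R to the table and to the list, and correct the count.
3. In Results, replace the empowerment wording with the instrument names. Give the change, 95% interval and paired N for every score, including the resiliency score by name. Label resiliency as outside the Aim 1 hypotheses and exploratory. If the final report already holds these figures, copy them in.
4. Only if neither PPS-R nor any other empowerment or needs instrument was collected, say that those two hypotheses rest on the qualitative and navigation data.

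No multiplicity adjustment is needed, so no power is lost. The cost is one short table, a dated note and a few reworded sentences, with no new data. The downside is a more cautious resiliency claim and visibly wide intervals: about plus or minus 0.37 SD of the change with 30 pairs, and wider with fewer.
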